7.6.3 Data Monitoring Committee

A DMC will be constituted for Study UX001-CL202 and will act in an advisory capacity to Ultragenyx to monitor the safety of SA-ER/SA-IR in subjects who participate in the study. The DMC may:

- Review plans for data monitoring.
- Evaluate the progress of the trial, study data quality, timeliness, subject recruitment, accrual and retention, subjects' risk versus potential benefit, and other factors that could affect the study outcome.
- Consider relevant information that may have an impact on the safety of the participants or the ethics of the study
- Make other recommendations to Ultragenyx concerning continuation, termination or other modifications of the study based on their observations of the study.

7.6.4 Determination of Sample Size

Approximately 46 subjects may be enrolled in Part I of this open-label extension study. Sample size is limited to the number of subjects enrolled in the Phase 2 safety and efficacy study, UX001-CL201. As Part I of the study is intended to evaluate of the long-term safety of 6g/day SA-ER in subjects with GNE Myopathy, and ascertain the long-term effect of SA-ER treatment on muscle strength, mobility, and functional disability, the sample size is deemed reasonable to satisfy Part I study objectives.

Approximately 10 treatment-naïve subjects will be enrolled into Part II of the study. This subset of treatment naïve GNE Myopathy subjects will provide additional safety and efficacy information following treatment with SA-ER/SA-IR.

The study design is open-label with all subjects receiving the same treatment. Therefore, the study is not powered to assess statistically significant comparisons. Instead, the sample size is intended to provide the maximum amount of long-term safety and efficacy data for the investigational product.

8 STUDY CONDUCT

8.1 Ethics

8.1.1 Institutional Review Board or Ethics Committee

The IRB/EC must be a properly constituted board or committee operating in accordance with 21 CFR Part 56, "Institutional Review Boards." This protocol, any protocol amendments, and the associated informed consent forms (ICFs) must be submitted to the IRB/EC for review and must be approved before screening of any subject into the study. Study drug may not be shipped to the investigator until Ultragenyx or its designee has received a copy of the letter or certificate of approval from the IRB/EC for the protocol and any protocol amendments, as applicable.

All subject recruitment and/or advertising information must be submitted to the IRB/EC and Ultragenyx or its designee for review and approval prior to implementation. IRB/EC approval of any protocol amendments must be received before any of the changes outlined in the amendments are put into effect, except when the amendment has been enacted to protect subject safety. In such cases, the chair of the IRB/EC should be notified immediately and the amendment forwarded to the IRB/EC for review and approval.

8.1.2 Ethical Conduct of Study

This protocol is written in accordance with the principles established by the 18th World Medical Association General Assembly (Helsinki, 1964) and subsequent amendments and clarifications adopted by the General Assemblies. The investigator will make every effort to assure the study described in this protocol is conducted in full conformance with those principles, current FDA regulations, ICH Good Clinical Practices (GCP) guidelines, and local ethical and regulatory requirements. Should a conflict arise, the investigator will follow whichever law or guideline affords the greater protection to the individual subject.

The investigator will also make sure he or she is thoroughly familiar with the appropriate administration and potential risks of administration of the study drug, as described in this protocol and the IB, prior to the initiation of the study.

8.1.3 Subject Information and Consent

Appropriate forms for documenting written informed consent will be provided by the investigator and reviewed and approved by Ultragenyx or its designee before submission to the IRB/EC. Ultragenyx or its designee must receive a copy of the IRB/EC's approval of the ICF before the shipment of study drug to the study site.

It is the investigator's responsibility to obtain signed written informed consent from each potential study subject prior to the conduct of any study procedures. This written informed consent will be obtained after the methods, objectives, requirements, and potential risks of the study have been fully explained to each potential subject. The investigator must explain

to each subject that the subject is completely free to refuse to enter the study or to withdraw from it at any time.

The method of obtaining and documenting informed consent and the contents of the ICF will comply with ICH GCP guidelines, the requirements of 21 CFR Part 50, “Protection of Human Subjects,” the Health Insurance Portability and Accountability Act (HIPAA) regulations, and all other applicable regulatory requirements. Subjects will be given a copy of the signed ICF and will be provided any new information during the course of the study that might affect their continued participation in the study. The investigator or a qualified designee will be available to answer each subject's questions throughout the study, and all of the subject's questions must be answered to the subject's satisfaction. If the protocol is amended and the ICF is revised, each subject will be required to provide written informed consent again using the revised ICF.

Receipt of written informed consent will be documented in each potential subject's CRF. The signed ICF will remain in each subject's study file and must be available to the study monitor(s) at all times.

8.2 Investigators and Study Administrative Structure

Each investigator must provide Ultragenyx and/or its designee a completed and signed Form FDA 1572 and a Financial Disclosure Form. All sub-investigators must be listed on Form FDA 1572 and Financial Disclosure Forms must be completed for all sub-investigators listed on Form FDA 1572.

Ultragenyx and/or its designee will be responsible for managing and monitoring the clinical trial to ensure compliance with FDA and ICH GCP guidelines. Ultragenyx's trained designated representative (the monitor) will conduct regular visits to the clinical site, to perform source document verification. The monitor will verify the investigator's ongoing qualifications, inspect clinical site facilities, and inspect study records, including proof of IRB/EC review, with the stipulation that subject confidentiality will be maintained in accordance with local and federal regulations, including HIPAA requirements.

A Coordinating Investigator has been identified for this trial. The Coordinating Investigator is selected on the basis of active participation in the trial, thorough knowledge of the therapeutic area being studied, and the ability to interpret data. The Coordinating Investigator reads and signs the Clinical Study Report (CSR).

8.3 Investigational Product Accountability

While at the clinical site, study drug must be stored in a secure limited access location at controlled temperature as described in the IB and according to product packaging. The storage facility must be available for inspection by the study monitor at any time during the study.

A drug accountability record must be maintained for all study drug received, dispensed, returned, designated for destruction, and/or lost during the study. This record must be kept current and made available to the study monitor for inspection. Following the close-out of the study, all unused study drug must be returned to Ultragenyx and/or its designee unless other instructions have been provided for final disposition of the study drug.

8.4 Data Handling and Record Keeping

8.4.1 Case Report Forms and Source Documents

The investigator is required to initiate and maintain, for each subject, an adequate and accurate case history that records all observations and other data related to the study for that subject. A validated electronic data capture (EDC) system will be used for entry of the data into electronic CRFs. Data must be recorded on CRFs approved by Ultragenyx or its designee. All information recorded on CRFs for this study must be consistent with the subject's source documentation.

Initial data entry and any changes to the data will be made only by Ultragenyx-authorized users, and data entries and changes will be captured in an electronic audit trail.

An explanation of any data change should be recorded in the CRF. All data entered in to the CRF must be verifiable; therefore, CRFs will be routinely checked for accuracy, completeness, and clarity and will be cross-checked for consistency with source documents, including laboratory test reports and other subject records by Ultragenyx or its designee. The investigator must allow direct access to all source documents.

8.4.2 Data Quality Assurance

Monitoring and auditing procedures developed by Ultragenyx and/or its designee will be implemented to ensure compliance with FDA and ICH GCP guidelines.

Ultragenyx's designated representative (the monitor) will contact the investigator and conduct regular visits to the study site. The monitor will be expected and allowed to verify the investigator's qualifications, to inspect clinical site facilities, and to inspect study records, including proof of IRB/EC review, with the stipulation that subject confidentiality will be maintained in accordance with local and federal regulations, including HIPAA requirements. The monitor will also be responsible for confirming adherence to the study protocol, inspecting CRFs and source documents, and ensuring the integrity of the data. CRFs will be checked for accuracy, completeness, and clarity and will be cross-checked for consistency with source documents including progress notes, laboratory test reports and other subject records. Instances of missing or uninterruptable data will be resolved in coordination with the investigator.

The monitor will also investigate any questions concerning adherence to regulatory requirements. Any administrative concerns will be clarified and followed. The monitor will maintain contact with the site through frequent direct communications with the study site by e-mail, telephone, facsimile, and/or mail. The investigator and all other site personnel agree

to cooperate fully with the monitor and will work in good faith with the monitor to resolve any and all questions raised and any and all issues identified by the monitor.

The investigator understands that regulatory authorities, the IRB/EC, and/or Ultragenyx or its designees have the right to access all CRFs, source documents, and other study documentation for on-site audit or inspection and will retain this right from the start of the study to at least two years after the last approval of a marketing application or for at least two years after clinical development of the study drug for the indication being studied has been discontinued. The investigator is required to guarantee access to these documents and to cooperate with and support such audits and inspections.

8.4.3 Record Retention

All study records must be retained for at least 25 years after the end of the clinical trial or in accordance with national law. Subject files and other source data must be kept for the maximum period of time permitted by the hospital, institution or private practice, but not less than 25 years. Ultragenyx must be notified and will assist with retention should the Investigator/institution be unable to continue maintenance of subject files for the full 25 years. All study records must be stored in a secure and safe facility.

8.5 Reporting and Follow-up of Adverse Events

8.5.1 Definition of Adverse Events

An AE is defined as any untoward medical occurrence associated with the use of a drug in humans, whether or not considered drug related. An AE can therefore be any unfavorable and unintended sign (including an abnormal laboratory finding, for example), symptom, or disease temporally associated with the use of a medicinal (investigational) product, whether or not related to the medicinal (investigational) products.

A suspected adverse reaction is any AE for which there is a reasonable possibility that the drug caused the AE. For the purposes of expedited safety reporting, “reasonable possibility” means there is evidence to suggest a causal relationship between the drug and the AE. Suspected adverse reaction implies a lesser degree of certainty about causality than adverse reaction, which means any AE caused by a drug.

Life-threatening AE or life-threatening suspected adverse reaction is an AE or suspected adverse reaction that, in the view of either the investigator or Ultragenyx, places the patient or subject at immediate risk of death. It does not include an AE or suspected adverse reaction that, had it occurred in a more severe form, might have caused death.

An SAE or serious suspected adverse reaction is an AE or suspected adverse reaction that at any dose, in the view of either the investigator or Ultragenyx, results in any of the following outcomes:

- Death

- A life-threatening AE
- Inpatient hospitalization or prolongation of existing hospitalization
- Persistent or significant incapacity or substantial disruption of the ability to conduct normal life functions
- A congenital anomaly/birth defect

Note that hospitalizations planned prior to study enrollment (e.g., for elective surgeries) are not considered SAEs. Hospitalizations that occur for pre-existing conditions that are scheduled after study enrollment are considered SAEs.

Important medical events that may not result in death, be immediately life-threatening, or require hospitalization may be considered serious when, based upon appropriate medical judgment, they may jeopardize the patient or subject and may require medical or surgical intervention to prevent one of the outcomes listed in the definition.

8.5.2 Severity of Adverse Events

Wherever possible, the severity of all AEs will be graded using the NCI CTCAE. The majority of AEs can be graded using this system.

If an AE cannot be graded using the CTCAE criteria, it should be graded as mild, moderate, severe, life-threatening, or death using the following definitions.

- ***Mild (Grade 1):*** Awareness of signs or symptoms, but easily tolerated and of a minor irritant type, causing no loss of time from normal activities. Symptoms do not require therapy or a medical evaluation; signs and symptoms are transient.
- ***Moderate (Grade 2):*** Events introduce a low level of inconvenience or concern to the participant and may interfere with daily activities, but are usually improved by simple therapeutic measures; moderate experiences may cause some interference with functioning.
- ***Severe (Grade 3):*** Events interrupt the participant's normal daily activities and generally require systemic drug therapy or other treatment; they are usually incapacitating.
- ***Life-threatening (Grade 4):*** Events that place the participant at immediate risk of death or are disabling.
- ***Death (Grade 5):*** Events that result in death.

To make sure there is no confusion or misunderstanding of the difference between the terms "serious" and "severe," which are not synonymous, the following note of clarification is provided. The term "severe" is often used to describe the intensity (severity) of a specific event (as in mild, moderate, or severe myocardial infarction); the event itself, however, may be of relatively minor medical significance (such as severe headache). This is not the same as "serious" which is based on subject/event outcome or action criteria usually associated

with events that pose a threat to a subject's life or functioning. Seriousness (not severity) serves as a guide for defining regulatory reporting obligations.

8.5.3 Relationship of Adverse Events to Study Drug

The investigator will assess the potential relationship of the AE to study drug using the following descriptions.

- **Not Related:** This category applies to an AE that is clearly not related to the investigational agent/procedure, beyond a reasonable doubt. That is, another cause of the event is most plausible; and/or a clinically plausible temporal sequence is inconsistent with the onset of the event and the exposure to study drug and/or a causal relationship is considered biologically implausible.
- **Possibly Related:** This category applies to an AE that follows a reasonable temporal sequence from administration of the study drug and that follows a known or expected response pattern to the suspected study drug, but that could readily have been produced by a number of other factors.
- **Probably Related:** This category applies to an AE that is likely related to the investigational agent/procedure. That is, the AE has a temporal relationship to the administration of the investigational agent(s) or research intervention, follows a known or suspected pattern of response, and is strongly associated with study drug exposure.

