7.3.3.1 Stopping Rules

A DMC will be constituted for Study UX001-CL202 and will act in an advisory capacity to Ultragenyx to monitor the safety of SA-ER/SA-IR in subjects who participate in the study (see Section 7.6.3). The DMC may provide advice to Ultragenyx in any determination of whether study enrollment should be paused or if the study should be halted.

AEs will be graded according to the National Cancer Institute Common Terminology Criteria for Adverse Events (NCI CTCAE). If two subjects develop the same unexpected Grade 3 AE that is possibly or probably related to study drug or any subject develops an unexpected Grade 4 AE that is possibly or probably related to study drug, enrollment of new subjects may be suspended until a thorough evaluation can be performed. Should these AEs occur, a full clinical evaluation will be performed by the medical monitor, principal investigators, and DMC in order to make a decision regarding what actions to take, including whether to suspend or resume enrollment, or recommend stopping the study after Institutional Review Board (IRB)/Ethics Committee (EC) review. The recommendations from the medical monitor and investigators will be forwarded to the IRB/EC for review and approval.

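### Possible relatedness requires a known or expected pattern, but the stopping rule counts only related AEs that are unexpected (a term left undefined), so some novel events fit no causality category

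*Protocol*

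**What the plan says.** Protocol 8.5.3 gives the investigator three categories.

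- **Possibly Related:** reasonable timing, and an event that "follows a known or expected response pattern to the suspected study drug", although other explanations are readily available.
- **Probably Related:** a temporal relationship, and an event that "follows a known or suspected pattern of response, and is strongly associated with study drug exposure".
- **Not Related:** "clearly not related to the investigational agent/procedure, beyond a reasonable doubt". The explanatory sentence adds events for which another cause is most plausible, the timing does not fit, or causation is biologically implausible.

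SAP 6.10.1, Table 11, repeats these definitions. Planned Table 14 (SAP 8.1) reports treatment-emergent AEs by relationship.

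Protocol 7.3.3.1 has two triggers. The first reads: "If two subjects develop the same unexpected Grade 3 AE that is possibly or probably related to study drug". The second needs only one subject, with a Grade 4 event that is likewise unexpected and falls in either of those two categories. If either trigger is met, "enrollment of new subjects may be suspended until a thorough evaluation can be performed". The section also says, in mandatory wording, that the medical monitor, principal investigators and DMC will carry out a full clinical evaluation, which can lead to a recommendation to stop the study.

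Unexpected is not defined in either document. Protocol 8.5.1 contains a separate causality standard, reasonable possibility, which rests on evidence suggesting a causal link and does not ask for a known pattern.

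**The concern.** The rule takes its relatedness terms from 8.5.3. The weaker of its two qualifying categories asks for an expected response pattern, while the rule asks for an unexpected event. A new toxicity often first appears as one or two cases with plausible timing and an uncertain cause, which is the level of evidence that Possibly Related would normally hold.

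Two things are at stake. A trigger that is not met does not call for the evaluation in 7.3.3.1. And the relationship summary in Table 14 may omit events for which a causal link is plausible. Both matter more because, as Protocol 7.2 says, Part II is the first time that patients with GNE myopathy receive the SA-ER/SA-IR combination.

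**Working it through.** The plan states no operating characteristic for the stopping rule, so there is no figure to reproduce. The main check sets the texts side by side.

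**Step 1. Test four kinds of event against 8.5.3.** All have plausible timing.

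| Event | Possibly | Probably | Not Related | Can it count towards 7.3.3.1? |
|---|---|---|---|---|
| A. Novel, suspected pattern, strongly associated with exposure | pattern not known | fits | no | yes |
| B. Novel, another cause most plausible | pattern not known | no strong association | fits | no, and none is intended |
| C. Novel, no most-plausible other cause, no strong association | fails on pattern | fails on association | not clearly unrelated | no category, so unclear |
| D. Known type of effect, unexpected only in severity | fits | may fit | no | yes, if unexpected includes severity |

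Only C falls through. Protocol 8.5.4.1 still requires a relationship to be recorded for every AE, so a C event must be forced into a category that does not describe it.

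**Step 2. Ask what else would catch a C event.** SAE reporting (8.5.4.2) and SUSAR reporting (8.5.4.4) apply to serious events. Protocol 8.5.2 stresses that severe and serious are different things. A Grade 3 event that is not serious therefore enters neither route. DMC review remains, but 7.1 describes it as periodic and ad hoc. For such events 7.3.3.1 holds the only numerical trigger in the documents.

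**Step 3. Illustrate the sensitivity of the trigger.** The sample size is 46 + 10 = 56 (Protocol 7.6.4). Two quantities are assumptions and are not in the documents: p, the true per-subject rate of one new drug-caused event that is regarded as unexpected; and c, the share of such events recorded as possibly or probably related. With subjects independent, the number counted is X ~ Binomial(56, p × c). The Grade 3 trigger is P(X ≥ 2) and the Grade 4 trigger is P(X ≥ 1).

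Example, p = 0.05 and c = 1: P(X = 0) = 0.95^56 = 0.0566; P(X = 1) = 56 × 0.05 × 0.95^55 = 0.1667. So P(X ≥ 2) = 1 − 0.0566 − 0.1667 = 0.777, and P(X ≥ 1) = 1 − 0.0566 = 0.943.

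| p | Trigger | c = 1 | c = 0.5 | c = 0.25 | c = 0 |
|---|---|---|---|---|---|
| 0.02 | Grade 3 | 0.309 | 0.108 | 0.032 | 0 |
| 0.02 | Grade 4 | 0.677 | 0.430 | 0.245 | 0 |
| 0.05 | Grade 3 | 0.777 | 0.410 | 0.155 | 0 |
| 0.05 | Grade 4 | 0.943 | 0.758 | 0.506 | 0 |
| 0.10 | Grade 3 | 0.980 | 0.777 | 0.410 | 0 |
| 0.10 | Grade 4 | 0.997 | 0.943 | 0.758 | 0 |

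The table shows how strongly the trigger depends on classification. It is not evidence that misclassification occurs or of how often. The c = 0 column is a bound; because events of types A and D can count, the documents do not imply it.

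**The case against.** The strongest reply is that the two texts are not opposites. Unexpected can be read as outside the AE profile seen so far, including in severity, and such an event can still follow a known drug response. Protocol 5.3 describes osmotic diarrhea in dogs at very high doses and more GI symptoms than placebo in the earlier Phase 2 study, so a GI event of unusually high grade could be both. Probably Related accepts a merely suspected pattern. Not Related already takes in events with a more plausible other cause. This all stands, and it narrows the problem to event C.

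The second reply is that safety does not hang on this rule. Suspension of enrollment is discretionary, and the synopsis already speaks of the additional subjects as enrolled. DMC advice, 24-hour SAE reporting, SUSAR reporting and the reasonable-possibility standard do not use the 8.5.3 categories. The SAP tables by system organ class, preferred term, severity, seriousness and discontinuation show events whatever their recorded relationship. This stands too, but it does not cover the non-serious Grade 3 event, and it does not replace the evaluation that 7.3.3.1 makes mandatory once a trigger is met.

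A reader might also infer that investigators will drift towards Not Related, so that Table 14 is biased downwards. The documents do not show this. That category demands clear unrelatedness beyond reasonable doubt, which pulls the other way. What can be said is that the wording gives no determinate answer.

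**Conclusion.** There is a real but partial conflict between Protocol 8.5.3 (with SAP Table 11) and Protocol 7.3.3.1. It affects one identifiable class of event: novel, plausibly timed, without a most-plausible alternative cause, and not strongly associated with exposure. Such an event has no category, may not count towards the trigger, and may not be shown as related in Table 14. The practical gap is clearest for non-serious Grade 3 events.

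Two stronger readings are tempting and should not be adopted. One is that an unexpected event can never be possibly related; this needs a definition of unexpected that the documents do not give. The other is that the trigger cannot fire for a new toxicity; the suspected-pattern clause in Probably Related contradicts it.

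The conclusion rests on reading the conditions in 8.5.3 as written, joined by *and*, and on the plain sense of unexpected. No frequency of affected events can be derived, and the probabilities above are conditional on assumed p and c. The point merits correction because it concerns safety monitoring and the remedy is mostly wording.

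**What to change.** Protocol 8.5.3, Protocol 7.3.3.1 and SAP Table 11 must be reconciled:

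1. Define unexpected as used in 7.3.3.1, stating how it relates to the pattern wording in 8.5.3 and whether it covers severity as well as type of event.
2. Reword the causality categories so that every AE falls into exactly one, and so that a known or expected pattern supports possible relatedness without being necessary for it. The reasonable-possibility standard in Protocol 8.5.1 already works this way.
3. Carry the same wording into SAP Table 11.

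The stopping thresholds and the actions that follow are for the sponsor and the DMC; no change to them is proposed here.

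The cost is a wording amendment to both documents and a notice to sites. There are two downsides. More events will be classed as possibly related. And AEs assessed before the change were judged on a different standard, so they must be flagged or re-assessed; otherwise Table 14 would mix the two.
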